1.4.2 Clinical Data

The Phase I, first-in-human (FIH) dose escalation study of NUC-1031 as a single-agent has been completed in patients with advanced solid tumors (PRO-001). The Investigator-sponsored study enrolled a total of 68 patients with advanced solid tumors between October 2012 and October 2014. The dose range tested was from 500-1,000 mg/m² in monthly cycles of administration, using a schedule derived from that used for gemcitabine (Day 1, 8 and 15 every 28 days).

The 68 patients treated on the study included 22 males and 46 females. The mean age of the patients was 56.3 years (range 20.3 to 83.5 years). The common cancer histories (>10%) included ovarian cancer (14.7%), pancreatic cancer (13.2%) and colorectal carcinoma (10.3%). The largest primary tumor (>30%) category was categorized as 'other', which included one patient with papillary serous carcinoma later classified as ovarian cancer. All the patients had been previously treated with chemotherapy with a mean (standard deviation) number of prior

chemotherapy regimens of 3.0 (1.77). A total of 34/68 patients (50.0%) received prior gemcitabine therapy. Across the range of doses tested on the study, the median number of NUC-1031 cycles received was 3 (range 0.3 to 19). A total of 14 patients received 6 or more cycles of treatment.

NUC-1031 was generally well tolerated. Although treatment emergent adverse events were reported in all patients, the majority were Grade 1 or 2 in severity, were reversible, and were considered unrelated to the study drug. Likewise, the majority of Grade 3 or 4 adverse events were considered unrelated to the study drug and resolved without sequelae.

The most commonly occurring treatment emergent and treatment related adverse events were laboratory abnormalities, specifically decreased blood cell counts (neutropenia, lymphopenia and thrombocytopenia), as well as elevations in liver function enzymes (alanine aminotransferase and aspartate aminotransferase). The most commonly occurring treatment related clinical adverse events were fatigue, nausea and vomiting and disturbance in taste (dysguesia). Within each cycle of therapy, these laboratory and clinical abnormalities were managed by withholding or delaying treatment. In addition, dose reductions were implemented in subsequent cycles of treatment for patients continuing on the protocol.

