4.2 Exclusion Criteria

Patients who meet any of the following criteria at Screening will be excluded from the study:

1. Disease classified as primary platinum refractory (*i.e.* progression while receiving initial line of platinum-based therapy or within 4 weeks of the initial regimen).
2. Received fewer than 3 prior chemotherapy-containing regimens.
3. Prior therapy with single-agent gemcitabine (prior gemcitabine plus carboplatin combination treatment is permitted).
4. Prior history of hypersensitivity to gemcitabine.
5. History of allergic reactions attributed to the components of the diluents used with NUC-1031.
6. Mucinous, low-grade serous, low-grade endometrioid, carcinosarcoma, clear cell, or undifferentiated/unclassifiable histology.
7. Symptomatic CNS or leptomeningeal metastases.
8. Prior chemotherapy, radiotherapy (other than short cycle of palliative radiotherapy for bone pain), treatment with a VEGF inhibitor, PARP inhibitor or immunotherapy within 21 days of first receipt of study drug (within 6 weeks for nitrosoureas and mitomycin C); hormone therapy within 14 days of first receipt of study drug; or blood transfusion, or use of any hematopoietic growth factors within 28 days of first receipt of study drug.
9. Residual toxicities from chemotherapy or radiotherapy, which have not regressed to Grade ≤ 1 severity (NCI CTCAE v4.03), except for neuropathy (Grade 2 allowed) or alopecia.
10. Patients who have a history of another malignancy diagnosed within the past 5 years, with the exception of adequately treated non-melanoma skin cancer or curatively treated carcinoma *in situ* of the cervix or ductal carcinoma *in situ* (DCIS) of the breast. Patients with previous invasive cancers are eligible if treatment was completed more than 5 years prior to initiating the current study treatment, and the patient has had no evidence of recurrence since then.
11. Presence of an uncontrolled concomitant illness or active infection requiring IV antibiotics.
12. Presence of any serious illnesses, medical conditions, or other medical history, including laboratory results, which, in the Investigator's opinion, would be likely to interfere with the patient's participation in the study, or with the interpretation of the results.
13. Known HIV positive or known active hepatitis B or C.

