9 DOSE MODIFICATIONS

Adverse events may be managed by dose delays and/or dose reductions according to the clinical situation. Advice on how to modify dosing for hematological and non-hematological toxicities is given below.

Only one dose reduction is permitted within a cycle. This may be a temporary dose reduction, in which case the next cycle can revert to the starting dose of the previous cycle, or it may be a permanent dose reduction which would apply to all subsequent cycles. Over the whole dosing period, each patient may have a maximum of 2 permanent dose reductions, after which treatment will be discontinued. The lowest dose which may be administered is 275 mg/m².

Treatment between cycles can be delayed for up to 14 days in order for patients to meet the re-treatment criteria before starting their next cycle. Patients who do not meet these requirements after this additional time will not be allowed to receive further cycles of NUC-1031 and will be withdrawn from the study.

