9.1 Hematological Toxicity – Dose Adjustment

NUC-1031 administration should be given according to the absolute neutrophil count (ANC) and platelet count on the day of dosing. On Day 1 of each 28-day cycle, if the ANC is $\geq 1.5 \times 10^9/l$ and the platelet count is $\geq 75 \times 10^9/l$, then NUC-1031 should be given at full dose unless the patient has previously been permanently dose reduced.

On Day 1 of each 28-day cycle, if the ANC is $1.5-1.0 \times 10^9/l$ and the platelet count is $50-75 \times 10^9/l$ without evidence of bleeding, then NUC-1031 should be given at a reduced dose unless the patient has received 2 prior dose reductions.

Within a cycle, should patients experience neutropenia or thrombocytopenia, dosing on Day 8 and Day 15 should be adjusted per [Table 2](#).

Table 2 Dose adjustments within a cycle (Days 8 and 15) based on ANC and platelet counts

ANC		Platelets	Starting dose (750 mg/m ²)	Starting dose (500 mg/m ²)	Starting dose (375 mg/m ²)
$\geq 1.5 \times 10^9/l$	AND	$\geq 75 \times 10^9/l$	750 mg/m ²	500 mg/m ²	375 mg/m ²
1.5-1.0 $\times 10^9/l$ and afebrile	AND/OR	50-75 $\times 10^9/l$ without evidence of bleeding	500 mg/m ²	375 mg/m ²	275 mg/m ²
$<1.0 \times 10^9/l$, or $<1.5 \times 10^9/l$ with fever	AND/OR	$<50 \times 10^9/l$, or $<100 \times 10^9/l$ with active bleeding	Omit	Omit	Omit

Should both the Day 8 and Day 15 doses be omitted for hematologic toxicity within the same cycle, the dose for all subsequent cycles should be permanently reduced to the next dose level.

If a patient starts a treatment cycle at 500 mg/m² and requires further dose reduction on Day 8 or Day 15 of the following cycle due to hematologic toxicity, dose modification should follow the column second from the right of [Table 2](#).

If a patient has her dose permanently reduced to 375 mg/m², and hematologic toxicity persists on any day that a dose is scheduled, dose modification should follow the far right column of [Table 2](#).

For all other hematologic toxicity, dose adjustments should be performed according to [Table 3](#).

Table 3 Dose adjustments for hematological toxicities (excluding toxicities relating to ANC and platelet counts)

NCI CTCAE grade	Dose adjustment
Grade 1 toxicity	If the patient was receiving 750 mg/m ² then reduce to 500 mg/m ² . If the patient was receiving 500 mg/m ² then reduce to 375 mg/m ² . If the patient was receiving 375 mg/m ² then reduce to 275 mg/m ² .

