Grade 2, 3 and 4 toxicity	Omit until resolution to \leq Grade 1 if the patient was receiving 750 mg/m ² then resume at the dose 500 mg/m ² . If the patient was receiving 500 mg/m ² then resume at the dose 375 mg/m ² . If the patient was receiving 375 mg/m ² then resume at the dose 275 mg/m ² .

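### Section 9.1 gives two dose instructions for a patient with adequate ANC and platelets and another Grade 1 hematologic toxicity, and Table 3's restart grade and reduction type are left unresolved

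*Protocol*

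**What the plan says.** - **Full-dose rule (Section 9.1, Day 1).** With ANC at least 1.5 and platelets at least 75 × 10⁹/l, "then NUC-1031 should be given at full dose unless the patient has previously been permanently dose reduced". An earlier permanent reduction is the only exception named. The first row of Table 2 gives the unreduced dose for the same counts on Days 8 and 15.
- **Table 3 (Section 9.1).** The section continues: "For all other hematologic toxicity, dose adjustments should be performed according to" Table 3, which is headed "Dose adjustments for hematological toxicities (excluding toxicities relating to ANC and platelet counts"). The Grade 1 row reads "If the patient was receiving 750 mg/m ² then reduce to 500 mg/m ²", with matching steps from 500 to 375 and from 375 to 275. The Grade 2-4 row omits dosing until the toxicity is at or below "Grade 1 if the patient was receiving 750 mg/m ² then resume at the dose 500 mg/m ²", again with matching lower steps.
- **Limits (Section 9).** "Only one dose reduction is permitted within a cycle". A reduction may be temporary, with the next cycle going back to the previous starting dose, or permanent. Two permanent reductions are the maximum, after which treatment ends.
- **Use of dosing intensity (Section 3.1).** The Part II dose is chosen on safety, dosing intensity, PK and clinical activity seen in Part I, with up to 20 patients per arm.

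**The concern.** A patient with adequate ANC and platelets and a Grade 1 hematologic toxicity of another kind falls under both rules. One gives the full dose, the other one level less. Nothing in the section says which governs.

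Table 3 has a second difficulty. Grade 1 is a state in which dosing may restart and also the state that calls for a reduction. Its third difficulty is silence on whether a reduction is temporary or permanent. Elsewhere the protocol does say: Section 9.1 makes the reduction permanent when both Day 8 and Day 15 are omitted for hematologic toxicity, and Section 9.2 makes it permanent after a non-hematologic omission.

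At stake is the Part I comparison. If sites resolve the text differently, the same blood result leads to different doses, and some of the difference in dosing intensity between 500 and 750 mg/m² reflects how the table was read and not how the drug was tolerated.

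**Working it through.** The protocol gives no figure of its own on this point, so the check follows the rules through and then sizes the consequence.

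**1. Both rules apply to one patient.** Take Day 1 of Cycle 2, ANC and platelets adequate, no earlier permanent reduction, new Grade 1 lymphopenia judged a drug-related toxicity, previous dose 750. The Section 9.1 sentence gives 750; the Table 3 Grade 1 row gives 500. On Day 8 or 15 the same clash arises with the first row of Table 2.

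**2. The restart overlap.**
- *Across cycles:* 750 on Day 1; Grade 2 on Day 8, omitted; Grade 1 on Day 15, resumed at 500; still Grade 1 at the next Day 1. The Grade 1 row, tied to the dose she was receiving, now gives 375. The per-cycle limit does not stop this, because a new cycle has begun.
- *Within a cycle:* Day 1 delayed for Grade 2, then given at Grade 1 at 500; still Grade 1 on Day 8. The Grade 1 row gives 375. If the Day 1 step counts in that cycle, this is a second reduction and Section 9 forbids it.

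A patient who restarts at Grade 0 and stays there meets neither problem.

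**3. Size of one and two steps** (dose levels 750, 500, 375, 275 from Table 3):

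| Steps | 750 arm | 500 arm | Gap (mg/m²) |
|---|---|---|---|
| 0 | 750 (100%) | 500 (100%) | 250 |
| 1 | 500 (500/750 = 66.7%) | 375 (375/500 = 75%) | 125 |
| 2 | 375 (50%) | 275 (55%) | 100 |

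**4. Two-cycle illustrations.** Assumption: Grade 1 begins at Cycle 1 Day 8, Table 3 is followed, and there is at most one step per cycle. Planned totals are 6 × 750 = 4,500 and 6 × 500 = 3,000 mg/m².

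| Reading | 750 arm | 500 arm |
|---|---|---|
| Persists, steps permanent | (750+500+500) + 3×375 = 2,875; 63.9% | (500+375+375) + 3×275 = 2,075; 69.2% |
| Persists, steps temporary | 1,750 + 3×500 = 3,250; 72.2% | 1,250 + 3×375 = 2,375; 79.2% |
| Resolves by Cycle 2 Day 1, step temporary | 1,750 + 3×750 = 4,000; 88.9% | 1,250 + 3×500 = 2,750; 91.7% |

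If the full-dose rule governs instead, the figure is 100% in every row. Under the permanent reading, both permitted permanent reductions have been used by Cycle 2 Day 1.

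**5. Effect on arm means.** Let a share *f* of each arm take one step. The 750 arm then averages 750 − 250*f*, the 500 arm 500 − 125*f*, and the gap is 250 − 125*f*.
- *f* = 10%: 725 and 487.5, gap 237.5
- *f* = 50%: 625 and 437.5, gap 187.5
- *f* = 90%: 525 and 387.5, gap 137.5

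The protocol gives no value for *f*. Section 1.4.2 puts "specifically decreased blood cell counts (neutropenia, lymphopenia and thrombocytopenia") among the commonest Phase I events, but without grade or frequency, and it does not name anemia there.

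**The case against.** The best reply is that Table 3 supplements the count rule. The Day 1 sentence speaks only of ANC and platelets. If it overrode everything else, it would also override the omission of doses for Grade 3/4 non-hematologic toxicity in Table 4, which nobody intends. This is a natural reading, but the text does not state it, and it leaves the restart overlap and the temporary-or-permanent question untouched.

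The second reply is that fewer patients are affected than the table suggests. Section 9 presents its content as advice, Section 8.5 ties adjustments to drug-related toxicity, and Section 12.2 counts abnormal laboratory values as AEs only under listed conditions. That narrows the exposure. It does not remove it: Table 3 is keyed to CTCAE grade, and a new, drug-related, clinically significant Grade 1 event still meets both rules.

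A reader might go further in four ways that the protocol does not support.
- *That the arms would not be delivered as randomized.* Section 8.5 assigns an initial dose followed by modification rules, so reductions belong to each arm's regimen. In the illustrations the arms narrow but stay ordered.
- *That residual Grade 1 toxicity at entry forces a reduction.* Exclusion 9 bars only "Residual toxicities from chemotherapy or radiotherapy, which have not regressed to Grade" 1 or lower, so Grade 1 is admitted. But Section 12.2 does not treat pre-existing conditions as AEs unless they worsen, and Table 3 speaks of a dose already being received. Whether baseline grades count is unclear, not settled.
- *That a patient is stepped down at every dose.* The one-per-cycle limit stands against this; the result is a contradiction, not a certain cascade.
- *That Table 3 is wrong because it is stricter than Tables 2 and 4.* How strict different toxicity rules should be is a clinical judgment, and different thresholds are not in themselves a contradiction.

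**Conclusion.** The point holds as an internal inconsistency in the dosing instructions, in three parts: no stated precedence between the full-dose rule and the Table 3 Grade 1 row; a restart grade that overlaps the reduction grade and can run into the per-cycle limit; and no statement whether Table 3 reductions are temporary or permanent, although that decides when treatment ends.

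The consequence is a risk to dosing intensity and to separation of the arms, not a demonstrated loss. For a patient who takes one Table 3 step, the dose is 66.7% (750 arm) or 75% (500 arm) of the starting dose. Over two cycles the 750 arm illustrations run from 64% to 89%; they assume onset at Cycle 1 Day 8, and the low end also needs persistence and permanent steps. It cannot be claimed that much of the 750 arm would move to 500, because no incidence is given. It matters here because up to 20 patients per arm inform a choice of dose that rests in part on dosing intensity.

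**What to change.** Reconcile the Section 9.1 text, Table 2, Table 3 and the Section 9 limits so that each blood result leads to one instruction. The revised text should state:

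- which rule governs when ANC and platelets are adequate and another hematologic toxicity is present;
- what happens at the doses after a restart if the toxicity is still Grade 1, and how that fits the one-reduction-per-cycle limit;
- whether Table 3 reductions are temporary or permanent, and so whether they count toward the maximum of two;
- whether a grade already present at baseline counts.

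The sponsor decides the clinical rule; this review takes no position on which grade should trigger a reduction or permit dosing. The cost is a protocol amendment to one table and the sentences around it, and a memo to sites. No patients or procedures are added.

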9.2 Non-Hematological Toxicity – Dose Adjustment

Dose adjustment should be performed according to [Table 4](#). If dose omission is required, treatment should be delayed until the toxicity has resolved to \leq Grade 1. If this occurs, subsequent doses should be permanently reduced, without re-escalation. For significant pulmonary complications (*e.g.* pneumonitis and acute respiratory distress syndrome), study treatment should be stopped.

Table 4 Dose adjustment for non-hematological toxicities

NCI CTCAE grade	Dose adjustment
Grade 0-2 toxicity or Grade 3 nausea/vomiting/ alopecia	100% dose (with escalation of anti-emetic prophylaxis for nausea and vomiting)
Grade 3/4 toxicity (except nausea/vomiting/alopecia)	Omit until resolution to \leq Grade 1 if the patient was receiving 750 mg/m ² then resume at the dose 500 mg/m ² . If the patient was receiving 500 mg/m ² then resume at the dose 375 mg/m ² . If the patient was receiving 375 mg/m ² then resume at the dose 275 mg/m ² .

9.3 Guidance for Dose Omissions

Table 5 outlines the guidance for omission of doses on Day 1, 8 or 15.

Table 5 Dose omission guidance

Day 1 missed dose	Day 8 missed dose	Day 15 missed dose
If the dose omitted was due to be on Day 1 of the next cycle, that cycle will not be considered to start until the day the first dose is actually administered to the patient (i.e. 1-2-3-Rest, X-1-2-3-Rest, etc).	Cycle continues per protocol, with one dose not given (i.e. 1-2-3-Rest, 1-X-3-Rest, 1-2-3-Rest, etc). Day 15 is administered as per cycle calendar if blood results permit.	That week becomes the week of rest. Next dose (if blood results permit) becomes Day 1 of a new cycle, and the patient is considered to have had a 21-Day cycle.

10 OTHER TREATMENTS (NON-IMP)

All prescription and non-prescription medications and therapies, including pharmacologic doses of vitamins, herbal medicines, or other non-traditional medicines, taken from 28 days prior to the first dose of NUC-1031 through the End of Treatment Visit must be recorded in the CRF. All prior anti-cancer therapies from initial diagnosis up until enrollment must be recorded in the CRF.

10.1 Support Medication

Patients may receive standard prophylactic medical treatment for nausea and vomiting. During treatment, patients will be reviewed on a weekly basis during the first cycle and on each day of treatment for subsequent cycles. Additional visits may be arranged at the Investigator's discretion. All support medication must be recorded in the CRF.

10.2 Hematopoietic Growth Factor Support

The prophylactic use of hematopoietic growth factors (*e.g.* G-CSF) is not permitted in cycle 1. However, the Investigator may prescribe G-CSF as treatment for Grade 3 or higher neutropenia according to local protocols and as prophylaxis after the first event of Grade 3 neutropenia or for any febrile neutropenic episode in order to enable the patient to continue on study. All hematopoietic growth factors used from 30 days prior to date of consent until 30 days after administration of last dose of NUC-1031 must be recorded in the CRF. Any blood or platelet transfusions should also be recorded in the CRF.

10.3 Concomitant Medication and Non-Drug Therapies

Concomitant medication may be given as medically indicated. All concomitant medication and non-drug therapies used from 30 days prior to date of consent until 30 days after administration of last dose of NUC-1031 must be recorded in the CRF.

10.3.1 Contraception Methods

Patients are assumed to be infertile as a consequence of treatment for their disease, or postmenopausal (12 months of amenorrhea).

If patients are not infertile or post-menopausal, they must agree to:

- Abstinence during her entire participation in the study and for 30 days post-last dose of study medication *or*
- Use **two** forms of contraception, one of which must be a barrier method and one must be a highly effective form (less than 1% failure rate if used consistently and correctly).

Acceptable barrier methods (which may not be considered highly effective):

- Male or female condom, with or without spermicide
- Cap, diaphragm or sponge with spermicide

Highly effective forms of contraception include:

- Oral, intravaginal or transdermal combined (estrogen and progestogen containing) hormonal contraception associated with inhibition of ovulation
- Oral, injectable, or implantable progestogen-only hormonal contraception associated with inhibition of ovulation
- Surgical sterilization (bilateral occlusion, vasectomized partner)
- Intrauterine device or intrauterine hormone-releasing system

These forms of contraception must be used from the time of signing consent, throughout the treatment period, and for 30 days following the last NUC-1031 dose administration. Oral or injectable contraceptive agents cannot be the sole method of contraception. Patients of childbearing potential must have a negative serum pregnancy test within 72 hours prior to the first study drug administration.

10.4 Prohibited Therapy and Concomitant Medications

Use of the following therapies is prohibited during the study:

- Cytotoxic chemotherapy
- Radiotherapy
- Immunotherapy including immunosuppressive therapy
- Radioimmunotherapy
- Hormone therapy (other than contraceptives, hormone-replacement therapy, or megestrol acetate)
- Biologic agents intended for the treatment of ovarian cancer (other than hematopoietic growth factors, which are allowed if clinically indicated and used in accordance with instructions provided in the package inserts)
- Any therapies intended for the treatment of ovarian cancer, whether approved by local regulatory authorities or investigational
- Drugs that are known to prolong QTc interval ([Appendix 1](#)).
- Live vaccines (must also be avoided for six weeks after last NUC-1031 dose administration).

11 TUMOR RESPONSE ASSESSMENTS

11.1 Tumor Measurements and Assessment of Disease Response

Patients must have at least one lesion that can be accurately assessed at baseline by CT, MRI or PET-CT (US only), which is suitable for repeated assessment in order to be eligible for this study. All known or suspected disease sites must be assessed at baseline by either CT, MRI or PET-CT (US only) scan. The same radiological methods at baseline must be used to follow lesions throughout the study. Disease must be measured according to RECIST criteria, with target and non-target lesions identified, measured and followed throughout the study ([Appendix 2](#)). Biopsied lesions should not be designated as target lesions for the purposes of RECIST.

Whenever possible, the same qualified physician will interpret results to reduce variability. Radiographic images will be maintained at the study center, and Investigator's findings will be filed in the patient's source documents.

In addition, digital copies of all radiographic images will be collected and stored in a central radiologic facility in order to allow for independent confirmation of the radiographic imaging results. Instructions for the collection, and submission of images are provided in a separate Imaging Manual.

Tumor measurements and disease response assessments are to be performed every 8 weeks (± 7 days) from C1D1. If the patient stops study treatment for reasons other than radiologically confirmed PD, tumor measurements and disease response assessments should continue every 8 weeks (± 7 days) from C1D1 thereafter until PD is radiologically confirmed.

Tumor measurements and disease response assessments also are to be performed any time disease progression is suspected.

Patients should not discontinue NUC-1031 because of raised CA125 or other clinical signs of PD until PD has been confirmed by RECIST.

CRs and PRs must be confirmed by repeated images at least 4 weeks after initial documentation.

In the case of SD, measurements must have met the SD criteria at least once after study entry at a minimum interval of not less than 6 weeks.

A third-party central imaging vendor will review all study-related imaging. The imaging vendor will not be responsible for assessing images in real-time to inform on patient treatment decisions. This responsibility will remain with the Principal Investigator at the site. Please refer to the Imaging Manual for details on submission and review of images.

